Group	N	Month 0	Month 3	Month 6																																					
A	6	Oral placebo	CN54gp140 +Oral placebo +I.M placebo	CN54gp140 +Oral placebo +I.M placebo																																					
B	6	Ad4-EnvCN54	CN54gp140 +Oral placebo +I.M placebo	CN54gp140 +Oral placebo +I.M placebo																																					
C	6	Ad4-EnvCN54	CN54gp140 + Ad4-EnvCN54 + I.M placebo	CN54gp140 +Oral placebo + I.M placebo																																					
D	6	Ad4-EnvCN54	CN54gp140 + Ad4-EnvCN54 +I.M placebo	CN54gp140 + Ad4-EnvCN54 +I.M placebo																																					
E	6	Oral placebo	CN54gp140 +MVA-CN54 +Oral placebo	CN54gp140 +MVA-CN54 +Oral placebo																																					
F	6	Ad4-EnvCN54	CN54gp140 +MVA-CN54 +Oral placebo	CN54gp140 +MVA-CN54 +Oral placebo																																					
G	6	Ad4-EnvCN54	CN54gp140 +MVA-CN54	CN54gp140 +MVA-CN54																																					

			+ Ad4-EnvCN54	+Oral placebo
H	6	Ad4-EnvCN54	CN54gp140 +MVA-CN54 + Ad4-EnvCN54	CN54gp140 +MVA-CN54 + Ad4-EnvCN54
	48			

Participants will be randomised for recruitment into groups A-H in Part 1. The number of Ad4-EnvCN54 administrations combined with either gp140 protein boosts (A-D) or co-administration of gp140 with MVA-CN54 (E-H) will vary. Groups A (CN54gp140 alone) and E (MVA-CN54/CN54gp140 alone) will serve as control groups to assess the added benefit of the Ad4 vector. Following completion of Part 1, each vaccine group (A-H) will be assessed for number of mucosal responders (mucosal antibody (rectal/genital/oral) as measured by ELISA), and titre (mucosal and systemic) of antigen specific binding antibody. The primary immunogenicity endpoint will be Week 26; Visit 9. The vaccine groups and regimes (one from B-D and one from F-H) that have the best positive response at this timepoint will be expanded in Part 2 of the study.

Based on data from the MUCOVAC2 study, in which participants received 3 intramuscular doses of CN54gp140 with GLA-AF adjuvant, we anticipate that there will be no mucosal responders in group A (although there will be detectable systemic IgG responses). Enrollment through to completion of the primary immunological assessment for each group will be 7 months.

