## 7.6 CLINICAL STUDY DESIGN

To identify an effective Ad4 based oral vaccine that promotes systemic and mucosal responses to the HIV-1 envelope glycoprotein, our group will adopt a two part adaptive clinical trial. The study will assist in rapidly screening the impact of different routes, combination regimes and boosting options to Ad4-EnvCN54, MVA-CN54 and CN54gp140 / MPLA, to augment systemic and mucosal antibody responses following initial priming with Ad4.

The study will enrol 48 participants to Part 1 and 12 participants in Part 2. Recruitment will select potential participants who are willing to undergo serial blood draws. Additional participants may be enrolled to replace any early withdrawals.

**In Part 1**, n=6 participants per group will be randomised to groups A-H (Table 1). This design varies the number of Ad4 administrations, from 1 to 3, combined with either CN54gp140 protein boosts (A-D) or co-administration of gp140 with MVA (E-H). Groups A (gp140 alone) and E (MVA-CN54/CN54gp140 alone) will serve as control groups to assess the added benefit of the Ad4 vector. Each vaccine group (A-H) will be assessed for number of mucosal responders (mucosal antibody (rectal/genital/nasal) as measured by ELISA), and titre (mucosal and systemic) of antigen specific binding antibody. Based on data from the MUCOVAC2 study, in which participants received 3 intramuscular doses of CN54gp140 with GLA-AF adjuvant, we anticipate that there will be no mucosal responders in group A (although there will be detectable systemic responses). Enrolment through to completion of the primary immunological assessment for each group will be 7 months.

**In Part 2**, the best regimes from A-D (Ad4-EnvCN54/CN54gp140) and E-H (Ad4-EnvCN54/MVA-CN54/CN54gp140) will be expanded to n=12 (additional n=6) in Part 2. Immune responses at the Primary Immunogenicity Endpoint (Week 26) will be analysed. Selection will be based on total number of responders. In the event that more than one group has the same number of responders, mucosal antibody titre will be used to rank groups to determine which to take forward to Part 2. Should mucosal titers be indistinguishable between groups, then serum antibody levels will be taken into consideration in the selection of groups to progress to Part 2.

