## 10 REGISTRATION & DISTRIBUTION INTO TREATMENT GROUPS

### 10.1 RANDOMISATION PRACTICALITIES

#### 10.1.1 PART 1

The enrolment visit will take place within 90 days after the screening visit and will be the same day as the first vaccination. Assessments and procedures will be undertaken according to the schedules in Table 2, and data entered on the CRF.

The study will use sentinel dosing as a safety precaution. The first 6 participants successfully enrolled into the trial will be sequentially pre-allocated to treatment groups B, C, D, F, G and H. The first participant will be enrolled to group B. The safety data for this participant will be reviewed at day 7 before enrolling the next participant to group C. This process will be repeated for the other groups. This will ensure an escalation of the number of Ad4-EnvCN54 administrations combined with either CN54gp140 protein boosts (B-D) or co-administered CN54gp140 and MVA-CN54 (F-H).

After the accumulated safety data (up to day 7) for the 6th participant has been reviewed, on their first day of dosing the remaining participants will be block randomised into groups as follows:

- Block 1 (n=10): A, A, B, C, D, E, E, F, G, H
- Blocks 2-6 (n=8/block): A, B, C, D, E, F, G, H

#### 10.1.2 PART 2

Six additional healthy participants per group will be recruited and randomised to the best two regimes from A-D (Ad4-EnvCN54/CN54gp140) and E-H (Ad4-EnvCN54/MVA-CN54/CN54gp140). The visits schedule for participants in Part 2 will be the same as that for participants in Part 1. Assessments and procedures will be undertaken according to the schedules in Table 2, and data entered on the CRF.

#### 10.1.3 PASS CRITERION FOR PART 2

The group selection for Part 2 is based on results generated from the primary immunogenicity endpoint (Week 26, Visit 9). In the event that more than one group has the same number of responders, mucosal antibody titre will be used to rank groups to determine which to take forward to Part 2. Should mucosal titers be indistinguishable between groups, then serum antibody levels will be taken into consideration in the selection of groups to progress to Part 2. The criterion for a positive mucosal response, and methods for ranking groups on the basis of mucosal and serum antibody titers, will be specified in the LAP. If any groups are associated with unacceptable product related adverse events, they will be discontinued from further study.

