The study will enrol an additional 6 participants to two groups in Part 2 (Table 2). The best regimes from groups A-D (Ad4-EnvCN54 /CN54 rgp140) and/or E-H (Ad4-EnvCN54/MVA-CN54/CN54 rgp140) (if meeting the pass criteria) will be expanded to n=12.

The pass criteria for mucosal responders will be analysed in the first 32 participants (first four participants from each dosing group) at week 26 (the primary immunogenicity endpoint). The primary pass criteria will assess IgA responses in rectal mucosal samples, whereby a group will be considered to have met the pass criteria if there is a mucosal IgA titre greater than 100 ng/mL in the rectal secretions of ≥2 participants within a group at week 26.

However, if none of the groups meet this criterion, the selection will be expanded to include IgA responses from other mucosal secretions (nasal, cervico-vaginal (female participants) and semen (male participants)).

In the event that none/more than one of the groups meet this criterion, the selection will be based on week 26 median serum IgG titres. Statistical analysis comparing across groups A-D and E-H will be performed using the Kruskal-Wallis Test with Dunn's correction for multiple comparisons.

In the event that there is no statistical significance observed, the vaccination groups with the least and greatest exposure to the vaccine products (A and D) will be expanded into part 2 to allow for greater assessment of safety data.

4 Vaccination Schedule – Part 1 & Part 2

The doses, methods and schedule of immunisation are described below.

Table 1: Schedule of Doses and Method of Vaccinations

PART I							PART II	
	Group	N	Month 0	Month 3	Month 6		N	Vaccinations 1,2,&3
ARM 1	A	6	Oral placebo	CN54gp140 + Oral placebo +I.M placebo	CN54gp140 + Oral placebo +I.M placebo		12	Selected dosage from Part I
	B	6	Ad4-EnvCN54	CN54gp140 + Oral placebo +I.M placebo	CN54gp140 + Oral placebo +I.M placebo			
	C	6	Ad4-EnvCN54	CN54gp140 + Ad4-EnvCN54 +I.M placebo	CN54gp140 + Oral placebo +I.M placebo			
	D	6	Ad4-EnvCN54	CN54gp140 + Ad4-EnvCN54 +I.M placebo	CN54gp140 + Ad4-EnvCN54 +I.M placebo			
ARM 2	E	6	Oral placebo	CN54gp140 + MVA-CN54 + Oral placebo	CN54gp140 + MVA-CN54 + Oral placebo			
	F	6	Ad4-EnvCN54	CN54gp140 + MVA-CN54 + Oral placebo	CN54gp140 + MVA-CN54 + Oral placebo			
	G	6	Ad4-EnvCN54	CN54gp140 + MVA-CN54 + Ad4-EnvCN54	CN54gp140 + MVA-CN54 + Oral placebo			
	H	6	Ad4-EnvCN54	CN54gp140 + MVA-CN54 + Ad4-EnvCN54	CN54gp140 + MVA-CN54 + Ad4-EnvCN54			
		48					max 12	

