A General Linear Mixed Model is employed using PROC MIXED statistical procedure in SAS systems, separately, considering each mucosal response variable as outcome variable, the arm (arm1 and arm2) as a fixed effect and gender (female and male) as a covariate. The participant will be used as a random effect. The denominator degrees of freedom are adjusted using the Kenward-Roger approximation.

An excerpt of the SAS code that will be used in part 2 is given below.

```

proc mixed data=data;
  class group gender;
  model response=arm gender/ddfm=kr;
  random participant;
run;

```

If data are found to be severely skewed, the non-parametric methods as described in section 12.2.1.1 in part 1 will be used to contrast response variables between arms (arm 1 and arm 2). In this case, gender cannot be included in the analysis.

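### On the SAP's fallback path both groups expanded into Part 2 (A and D) belong to Arm 1, so the planned Arm 2 versus Arm 1 analysis cannot be computed; the selection steps leading there also differ from the protocol's

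*SAP*

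**What the plan says.** SAP 3.2 sets out a sequence.

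1. The pass mark for a group reads: "mucosal IgA titre greater than 100 ng/mL in the rectal secretions of ≥2 participants within a group at week 26". This is judged in the "first 32 participants (first four participants from each dosing group").
2. If no group passes, IgA at the other mucosal sites is brought in.
3. If "none/more than one of the groups meet this criterion, the selection will be based on week 26 median serum IgG titres". Groups are compared across A-D and E-H by Kruskal-Wallis with Dunn's correction.
4. If nothing is significant, "the vaccination groups with the least and greatest exposure to the vaccine products (A and D) will be expanded into part 2". The stated purpose is more safety data.

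SAP 3.1 places A-D in Arm 1 and E-H in Arm 2, and names A as a control without Ad4. SAP 12.2.1.2 then analyses 24 participants, 12 from each expanded group, in a mixed model with "the arm (arm1 and arm2) as a fixed effect". The rank-test alternative is also between arms, and example Table 1.2 reports the effect as Arm 2 against Arm 1.

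The protocol (Section 2, 7.6 and 10.1.3) selects first on how many participants in each group respond. Its tie-break reads: "In the event that more than one group has the same number of responders, mucosal antibody titre will be used to rank groups". Serum is considered only if mucosal titres cannot be told apart. It has no significance test in the selection and no A and D fallback. On eligible groups, its Section 2 Study Design takes one group out of B-D and another out of F-H, while 7.6 says "the best regimes from A-D (Ad4-EnvCN54/CN54gp140) and E-H (Ad4-EnvCN54/MVA-CN54/CN54gp140) will be expanded to n=12".

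**The concern.** The selection rule and the Part 2 analysis do not fit together. The rule has a prespecified branch in which both expanded groups come from one arm, but the only quantitative between-group analysis written for Part 2 needs one group from each. On that branch the week 26 antibody-level comparison, part of the primary immunogenicity analysis, has no valid specification. SAP 12.3 and 12.4 apply the same methods to the secondary and exploratory endpoints, so the gap carries over to them. An analyst would have to invent the contrast after seeing which groups were expanded.

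The route into that branch also departs from the protocol. Several groups passing on mucosal response sends the choice to serum, whereas the protocol would rank those groups on mucosal titre first.

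**Working it through.** **Counts.** The SAP's own figures reproduce: 8 groups x 4 = 32 for the pass criterion, and 2 x (6 + 6) = 24 for the Part 2 analysis.

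**Can the arm effect be estimated?** The model has an intercept, arm and gender, so three fixed-effect columns (both genders assumed present).

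| Expanded groups | Arm 1 n | Arm 2 n | Rank of matrix | Arm effect |
|---|---|---|---|---|
| One per arm | 12 | 12 | 3 of 3 | estimable |
| A and D | 24 | 0 | 2 of 3 | not estimable |

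With A and D, arm is the same for everyone and cannot be separated from the intercept. The rank test has only one sample. Arm 2 groups from Part 1 (six each) do not help, because SAP 12.2.1.2 limits the set to the two expanded groups. This result needs no numerical assumption about the data.

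**Exposure, counted from Table 1 (active administrations).** D: 3 Ad4 + 2 gp140 = 5. H: 3 Ad4 + 2 gp140 + 2 MVA = 7. A: 2 gp140 = 2. A is the least exposed, but D is the most exposed only within Arm 1.

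**Eligible groups, side by side.**

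| Place | Arm 1 set | Arm 2 set |
|---|---|---|
| Protocol 2 (Study Design), 11.1 | B-D | F-H |
| Protocol 2 (Vaccine Schedule for Part 2) | A-D | F-H |
| Protocol 7.6, 10.1.2; SAP 5.2 | A-D | E-H |
| SAP 3.2 | A-D | and/or E-H |
| SAP 3.2 fallback | A and D | none |

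**How often might more than one group pass?** The documents give no response rate, so p per participant is assumed, equal in the Ad4 groups and zero in A and E. P(a group passes) = 1 - (1-p)^4 - 4p(1-p)^3, followed by a binomial over groups.

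| p | P(group passes) | P(>1 of the 3 Ad4 groups in an arm) | P(>1 of all 6) |
|---|---|---|---|
| 0.2 | 0.181 | 9% | 30% |
| 0.3 | 0.348 | 28% | 68% |
| 0.5 | 0.688 | 77% | 99% |

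The SAP does not say whether passing groups are counted per arm or overall.

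**How often is the serum test non-significant?** Simulated Kruskal-Wallis, assuming alpha 0.05 and normal log titres. One-arm rows: four groups, one of which differs from the other three by the stated shift. Eight-group rows: A and E against six equally shifted groups.

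| Test | n per group | 1 SD | 2 SD |
|---|---|---|---|
| One arm, 4 groups | 4 | 85-86% | 47% |
| One arm, 4 groups | 6 | 72% | 15% |
| One test, 8 groups | 4 | 82% | 22% |
| One test, 8 groups | 6 | 60% | 2% |

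If there are two independent arm-wise tests and the fallback needs both to be non-significant, the 1 SD figures become 0.855 x 0.855 = 73% (n=4) and 0.72 x 0.72 = 52% (n=6). At 2 SD they are 0.47 x 0.47 = 22% and 0.15 x 0.15 = 2%. SAP 3.2 does not state whether there is one test or two, the alpha, or what follows if only one arm is significant.

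**The case against.** Four stronger readings are tempting, and the documents do not support them.

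- A reader might infer that several passing groups lead straight to A and D. They do not. Selection on serum IgG comes first, and a significant result there could still give one group per arm.
- A reader might infer that no Part 2 immunogenicity analysis survives. SAP 12.2.1 specifies responder proportions with confidence intervals and Fisher's test by vaccination group, and applies them to both parts. These can be run for A against D.
- A reader might infer that the rule will usually miss the best mucosal regimens. That rests on assumed response rates and on counting passes over all groups; per arm at 30%, more than one passes only 28% of the time. The serum step could be meant as a tie-break among passing groups, although the SAP does not say so. The protocol leaves ranking methods to the Laboratory Analysis Plan, which is not among the documents, and the decision to the Trial Management Group. Serum may also pick the same regimen.
- A reader might infer that exactly one winner per arm is required. SAP 3.2 says and/or, and the protocol's Group selection entry allows for a single expanded group.

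The case for leniency goes further. The fallback has a stated safety purpose, and safety is also a primary endpoint. The protocol disclaims confidence about group differences (14.3). Selecting on rectal IgA while SAP 10.1.1 gives nasal samples primary importance is not in itself an error, because a selection marker need not be the final endpoint. The four-per-group limit is attached to the mucosal pass criterion and is not stated for the serum test, although the protocol summary also speaks of 32 participants for week 26 immunogenicity. Finally, the SAP was signed in July 2021 and describes trial conduct in the past tense, so selection may already have been made.

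All of this stands, and it narrows the point. It does not make the arm contrast computable when A and D are expanded.

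**Conclusion.** The concern holds in a limited form. On one prespecified path, the Part 2 mixed model, its rank-test alternative and the Table 1.2 effect cannot be computed (24 v 0). This follows from the SAP's definitions alone. It is equally plain that SAP 3.2 turns to serum where the protocol would rank on mucosal titre, that the fallback's description of D conflicts with Table 1 (5 administrations against 7 for H), and that the eligible groups are stated inconsistently.

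The chance of reaching the fallback is not fixed by the documents. Once the serum step is reached, the tabulated non-significance rates run from 2% to 86% across the assumed effect sizes, group sizes and test structures. At 1 SD the fallback is more likely than not in every version shown; at 2 SD it is not.

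This should be fixed. It does not invalidate the trial, because the by-group responder analysis remains and the repair is to wording.

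**What to change.** 1. In SAP 12.2.1.2 and Table 1.2, define the Part 2 contrast, for both model and rank test, by expanded group instead of arm. The SAS excerpt already declares group as a class variable; the model statement should use it in place of arm. If one group per arm is expanded, group and arm coincide and nothing changes. If only one group is expanded, state that results are descriptive.
2. Reconcile SAP 3.2 and 5.2 with protocol 10.1.3 and with Table 1, and state one eligible set of groups throughout. Reconcile the exposure description in the fallback with Table 1.
3. If selection has not been made, rank groups within each arm on point estimates in the protocol's order (responders, mucosal titre, serum), without a significance gate. If it has been made, record the rule actually applied and the groups expanded, and leave the rule itself unrewritten.

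Cost: SAP wording and a protocol clarification. No extra participants or samples.

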Part 2 is dependent upon Part 1 and is designed to study groups selected on performance in part 1 in an expanded number of subjects. Data from both stages will be combined for safety and immunological analyses.

3 Study Design

To identify an effective Ad4 based oral vaccine that promotes systemic and mucosal responses to the HIV-1 envelope glycoprotein. This study will adopt a two-part adaptive clinical trial.

The study will assist in rapidly screening the impact of different routes, combination regimes and boosting options to Ad4-EnvCN54, MVA-CN54 and CN54gp140 / MPLA, to augment systemic and mucosal antibody responses following initial priming with Ad4.

This is a phase I trial in healthy male and female participants. The study will enrol 48 participants to Part 1 (6 in each group) and 12 participants in Part 2. Recruitment will select potential participants who are willing to undergo serial blood draws. Additional participants may be enrolled to replace any early withdrawals.

The clinical trial was conducted at the NIHR Imperial Clinical Research Facility (ICRF) at Hammersmith Hospital, London.

3.1 Part 1

In Part 1, n=6 participants per group will be randomised to groups A-H (Table 1). This design varies the number of Ad4 administrations, from 1 to 3, combined with either CN54gp140 protein boosts (A-D) or co-administration of gp140 with MVA (E-H).

Arm 1 (Groups A-D): Depending on the allocation of groups, participants will receive Ad4-EnvCN54 or placebo orally, CN54gp140/MPLA, and placebo I.M injections at month 0 (Week 0), 3 (Week 12) & 6 (Week 24).

Arm 2 (Groups E-H): Depending on the allocation of groups, participants will receive Ad4-EnvCN54 or placebo orally, CN54gp140/MPLA and MVA-CN54 I.M injections at month 0 (Week 0), 3 (Week 12) & 6 (Week 24).

Groups A (gp140 alone) and E (MVA-CN54/CN54gp140 alone) will serve as control groups to assess the added benefit of the Ad4 vector. Each vaccine group (A-H) will be assessed for number of mucosal responders (mucosal antibody (nasal/rectal/genital) as measured by ELISA), and titre (mucosal and systemic) of antigen specific binding antibody.

Enrolment through to completion of the primary immunological assessment for each group will be 7 months.

3.2 Part 2

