
5 Randomisation

5.1 Part 1

The study will use sentinel dosing as a safety precaution. The first 6 participants successfully enrolled into the trial will be sequentially pre-allocated to treatment groups B, C, D, F, G and H. The first participant will be enrolled to group B. The safety data for this participant will be reviewed at day 7 before enrolling the next participant to group C. This process will be repeated for the other groups. This will ensure an escalation of the number of Ad4-EnvCN54 administrations combined with either CN54gp140 protein boosts (B-D) or co-administered CN54gp140 and MVA-CN54 (F-H).

After the accumulated safety data (up to day 7) for the 6th participant has been reviewed, on their first day of dosing the remaining participants will be block randomised into groups as follows:

- Block 1 (n=10): A, A, B, C, D, E, E, F, G, H
- Blocks 2-5 (n=8/block): A, B, C, D, E, F, G, H

5.2 Part 2

Participants will be randomised to the groups chosen for expansion. Participants will be blind to the vaccine regime group to which they have been assigned. The laboratory undertaking immunological analysis will also be blinded to group and dosing regimen to prevent bias in analysis.

Six additional healthy participants per group will be recruited and randomised to the best two regimes from A-D (Ad4-EnvCN54/CN54gp140) and E-H (Ad4-EnvCN54/MVACN54/CN54gp140).

The visits schedule for participants in Part 2 will be the same as that for participants in Part 1.

6 Blinding

This is a single-blind, randomised trial with placebo controls. Participants will be block-randomised centrally, using the randomisation schedule produced by the statisticians at the Surrey CTU, to the study groups shown in Table 1, using a computer-generated algorithm with a back-up manual procedure. Randomisation will be stratified on the basis of gender.

All participants in Part 1 and Part 2 will be blinded to the vaccine regime group to which they have been assigned. The laboratory teams undertaking immunological analysis will also be blinded to group and dosing regimen to prevent bias in analysis. The clinical team will remain unblinded to the vaccine regime of trial participants throughout.

7 Replacing Withdrawals

As the number of participants per group is small and hence each participant is essential to the study, those who withdraw from the study will be replaced before completion of the week 26 visit.

8 Study hypothesis

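### The SAP 3.2 fallback calls D the greatest-exposure group although Table 1 gives H more, and with A and D both in Arm 1 the quantitative Part 2 arm contrast cannot be estimated

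*SAP*

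**What the plan says.** SAP 3.2 selects the groups for Part 2 in steps: rectal IgA, then IgA at other mucosal sites, then serum IgG. If the serum comparison shows no significance, "the vaccination groups with the least and greatest exposure to the vaccine products (A and D) will be expanded into part 2". The stated purpose is "to allow for greater assessment of safety data". The selection text in protocol sections 7.6 and 10.1.3 contains no such fallback. SAP 5.2 describes Part 2 as the best two regimes from A-D and E-H.

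SAP Table 1 sets out the schedules. At months 3 and 6, group A has "CN54gp140 + Oral placebo +I.M placebo", group D has "CN54gp140 + Ad4-EnvCN54 +I.M placebo" and group H has "CN54gp140 + MVA-CN54 + Ad4-EnvCN54". At month 0, A receives oral placebo, and D and H receive Ad4-EnvCN54. SAP 3.1 defines the arms: "Arm 1 (Groups A-D): Depending on the allocation of groups, participants will receive Ad4-EnvCN54 or placebo orally, CN54gp140/MPLA, and placebo I.M injections". Arm 2 is groups E-H, the MVA-CN54 groups.

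For Part 2, SAP 12.2.1.2 analyses 24 participants, 12 in each of two groups. The mixed model takes "the arm (arm1 and arm2) as a fixed effect and gender (female and male) as a covariate". If the data are severely skewed, a rank test between the two arms replaces it. The Table 1.2 shell has one column for each arm and reports Arm 2 against Arm 1.

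**The concern.** There are two separate problems. First, the pair named does not match its description. H's schedule contains all of D's and adds MVA-CN54, so a reader cannot tell whether the sponsor meant the extremes of all eight groups or the extremes of Arm 1. This matters because exposure is the criterion for choosing the pair and safety is the reason given.

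Second, both named groups belong to one arm, while the quantitative Part 2 analysis is written entirely as a contrast between arms. If the fallback were used, the planned model would have no treatment term to estimate, and the replacement would have to be chosen after the groups were known. SAP 12.3 and 12.4 send the secondary and exploratory endpoints to the same methods, so the gap would carry through to them.

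**Working it through.** **1. Exposure.** Active administrations counted from SAP Table 1 (months 0, 3 and 6 together):

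| Group | Arm | Ad4-EnvCN54 | CN54gp140 | MVA-CN54 | Total |
|---|---|---|---|---|---|
| A | 1 | 0 | 2 | 0 | 2 |
| B | 1 | 1 | 2 | 0 | 3 |
| C | 1 | 2 | 2 | 0 | 4 |
| D | 1 | 3 | 2 | 0 | 5 |
| E | 2 | 0 | 2 | 2 | 4 |
| F | 2 | 1 | 2 | 2 | 5 |
| G | 2 | 2 | 2 | 2 | 6 |
| H | 2 | 3 | 2 | 2 | 7 |

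A is the least exposed. D is not the most exposed: H exceeds it by 7 − 5 = 2 administrations, G exceeds it by 1, and F equals it.

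**2. Other readings of exposure.**
- Distinct products: A has 1; B, C, D and E have 2; F, G and H have 3. D is not the maximum.
- Ad4 doses only: A and E have 0; D and H have 3. D ties with H.
- Arm 1 only: A (2) is lowest and D (5) is highest. This is the only reading under which D is the sole maximum.

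**3. Safety information on H's schedule.** Under the fallback, A and D each go from 6 to 12, and H stays at 6. For 0 events in n, the two-sided 95% Clopper-Pearson upper limit is 1 − 0.025^(1/n):
- n=6: 1 − 0.025^(1/6) = 45.9%
- n=12: 1 − 0.025^(1/12) = 26.5%

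Protocol Table 7 prints 39% for 0 of 6. That is the one-sided limit, 1 − 0.05^(1/6) = 39.3%. The two-sided value is used here.

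The chance of seeing at least one event is 1 − (1 − p)^n. The documents give no event rate, so p is assumed:

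| Assumed p | n=6 | n=12 |
|---|---|---|
| 5% | 26% | 46% |
| 10% | 47% | 72% |
| 20% | 74% | 93% |

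Part 2 would add no MVA-CN54 recipients. The number stays at the 4 × 6 = 24 from Part 1.

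**4. What the fallback does add.** Recipients of three Ad4 doses rise from 12 (D 6 + H 6) to 18 (D 12 + H 6). The 0-event upper limit falls from 26.5% to 1 − 0.025^(1/18) = 18.5%.

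**5. Estimability.** The SAP's Part 2 total reproduces: 2 × (6 + 6) = 24. The fixed-effect columns are intercept, arm and gender. With A and D expanded, 24 participants are in Arm 1 and 0 in Arm 2, so the arm column is constant. The design has rank 2 of 3, taking both genders to be present, and the arm coefficient is not estimable. The rank-test alternative has only one class to compare. Cervico-vaginal and semen outcomes use only the women or only the men among the 24. Arm is constant in those subsets too, so the contrast fails for all four sites and both isotypes. With group (A or D) in place of arm, the same matrix has rank 3 for nasal and rectal outcomes, provided gender is not fully aligned with group.

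**The case against.** The strongest reply is that little is lost. Three parts of it stand.

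- **A Part 2 primary test survives.** A reader might infer that the fallback leaves Part 2 with no treatment comparison. It does not. SAP 12.2.1 specifies Fisher's exact test of responder status by vaccination group, for each site and isotype, in both parts, and that test works for A against D. Part 1 also keeps 24 participants in each arm.
- **The safety aim is not missed outright.** A reader might infer that it is. A and D both double, D ties with H on Ad4 doses, and protocol 7.8 says there are no clinical data yet for Ad4-EnvCN54. SAP section 2 combines safety data from both parts. The shortfall is confined to H's schedule and the MVA-CN54 combinations.
- **The SAP already leans towards group.** The CLASS statement lists group, and the Table 1.2 footnote refers to a group coefficient. The MODEL statement, the rank-test sentence and the Table 1.2 columns still say arm, so the inconsistency needs settling.

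A reader might also infer from the counts that A and H is the correct pair. The documents do not establish that. The sponsor may have intended the Ad4 range without MVA-CN54, and expanding H instead of D would leave D at 6. The rule is also the last step of a conditional sequence, in a trial that disclaims confidence about group differences (protocol 14.3).

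**Conclusion.** The point holds in limited form and should be fixed. The description of D as the greatest-exposure group contradicts SAP Table 1 on total administrations (5 against 7 for H) and on distinct products (2 against 3). It is right only under an unstated restriction to Arm 1. If the fallback is used, the safety reason is served for A, D and three-dose Ad4 exposure. It is not served for H's schedule, where the 0-event limit stays at 45.9% rather than 26.5%, or for MVA-CN54 combinations. The Part 2 quantitative primary contrast would be undefined for every site and isotype, while the responder test would be unaffected.

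This rests on counting each active administration once and on the Part 2 model using only the 24 participants of the two expanded groups, as SAP 12.2.1.2 states. The consequences arise only if selection reaches the fallback; no probability is claimed for that.

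**What to change.** 1. In SAP 3.2, reconcile the label and its stated reason with Table 1, and the fallback with SAP 5.2. Either the pair or the description has to change. Which groups to expand is the sponsor's decision.
2. Whatever is decided, replace arm by group in the Part 2 MODEL statement and its description, in the rank-test alternative, and in the Table 1.2 columns and contrast. If one group comes from each arm, group and arm coincide and the analysis is unchanged. If both come from one arm, the contrast now exists.

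The SAP is signed in July 2021 and describes the trial's conduct in the past tense, so the expansion may already have been decided. Item 1 would then be a matter of recording the reason correctly. Item 2 would still be needed before the Part 2 analysis.

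The cost is SAP wording and one model term, with no extra participants or samples.
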